7.8. Acceptability Study

Acceptability of the intervention to children will be assessed by the number of sessions attended and data collected from the interventionist and parent as we do not want to overburden the participants at each session. We will design a survey to assess acceptability of the intervention to the parents and the interventionists at the 20 week time point. In addition to this, acceptability will be further assessed through qualitative interviews, conducted by telephone with a purposive sample of 20% of the interventionists across school types (primary/secondary and sociodemographic variables) post-intervention (n=12).

These interviews will explore experiences of the implementation and delivery of LEGO®-based therapy, using Normalisation Process Theory (NPT) (May *et al.*, 2007) as the underpinning theoretical framework. Interventionists will also be asked to feedback on the perceived acceptability to children, parents and the school. We will use the interviews to investigate arising topics from the parent and interventionist surveys in more depth.

7.9. Qualitative Analysis

A nested qualitative analysis will be conducted near the end of the study. We will interview 12 interventionist teachers/ TAs to explore the arising topics from the parent and interventionist acceptability questionnaires. For the interviews we will use Normalisation Process Theory (NPT) (May *et al.*, 2007) to guide data collection and to frame the analysis to understand how easy it is to implement these interventions into routine practice. NPT conceives making changes in established routines as a complex and dynamic enterprise, and proposes a model which explains the way in which new practices are adopted and absorbed by individuals into existing behavioural conventions and routines. It has been proposed that this can help identify whether interventions are likely to become embedded and integrated as part of routine practice or not (Murray *et al.*, 2010). All interviews will be recorded and transcribed verbatim.

The Framework analysis approach (Spencer *et al.,* 2003) will be used to structure and explore the interview data, and NVivo software will be used to support this process.

7.10. Fidelity Analysis

We will develop a protocol for ensuring and monitoring intervention fidelity and sustainability. This will be composed of the following mechanisms:

- 1. An abridged training manual will be developed based on the existing LEGO®-based therapy manual (LeGoff *et al.*, 2014).
- 2. The training manual will be used to inform a programme of training developed and delivered by [name] (co-applicant and co-author of the LEGO®-based therapy manual).
- 3. Supervision teleconferences will be arranged between the trainers and [name] on a monthly basis.
- 4. The content of the treatment sessions will be monitored by video recording a purposively sampled number of schools with full written consent from all group participants.
 - a. We will record 72 (10%) of the sessions across the study and sample according to school level (primary/secondary) and sociodemographic variables.
 - b. 72 sessions across 24 schools, with three sessions per school recorded (one of the first four sessions, one of the second four sessions and one of the last four sessions).
 - c. To assess the fidelity of the intervention, the video sessions will be reviewed by two independent observers and the inter-rater reliability calculated.
 - d. The content of the recorded therapy sessions will be monitored using a recording form (fidelity checklist) based on work by [name].
 - e. This checklist will also be completed by the interventionist at the end of each session providing data on the content of the sessions. This self-reported data will be compared to the recorded sessions where available.

7.11. Economic Evaluation

Information about the cost of all aspects of the treatment will be collected including training costs. We will undertake an analysis of cost-effectiveness at the end of the trial by comparing the cost of the intervention with any treatment benefit. We will collect data from the participant's associated parent about their resource use, such as visits to their GP and visits to other health

and other social care providers and data from the associated TA about service use in school. We will collect data on these carer costs through our resource use questionnaire. These will include cost of productivity loss and out-of-pocket expenditures.

8. Study Intervention

8.1. LEGO®-Based Therapy

LEGO®-based therapy (LeGoff, [name] De La Cuesta, Krauss, & Baron-Cohen, 2014) is a group intervention that has gained considerable attention in the UK. The potential benefits of this therapy are that it was designed for school-age children with ASD as opposed to being an adapted form of a more generic social skills training intervention. Using collaborative LEGO®-based play the intention is to harness the child's own interests and so motivate learning and change, a focus recommended by international researchers in this area (LeGoff et al., 2014). LEGO® is a predictable, systematic multi-level construction toy that provides intrinsically structured tasks that children with ASD are highly motivated to complete (Owens, Granader, Humphrey, & Baron-Cohen, 2008). LEGO®-based therapy is specifically designed to make social interactions interesting to the child with ASD so that they learn how to play co-operatively with a toy that they enjoy which in turn increases the likelihood that they can continue to use these skills in their daily functioning.

Participating children allocated to the intervention group will be invited to attend a weekly group by a teacher or TA professionally trained in LEGO®-based therapy for a period of approximately 12 weeks. There may be breaks in the 12 weekly sessions due to illness and school holidays, though a break over the longer summer holiday will be avoided. In LEGO®based therapy, the task of constructing a LEGO® set is divided into different roles, such that social interaction is necessary to participate. Rather than building alone, children build in pairs or threes. One child acts as the 'Engineer' (describes the instructions), one is the 'Supplier' (finds the correct bricks) and the other is the 'Builder' (puts the pieces together). Children play their role for a certain length of time, or a certain number of steps in the instructions and then swap around. This division of labour with a common purpose requires children to practice many social communication skills such as joint attention, turn taking, sharing, joint problem solving and compromise. More structured play is followed by 'Freestyle' LEGO® activities in which children work in pairs or small groups to create a model from general LEGO® pieces without instructions. This provides opportunities for children to practice creativity, compromise, expressing their ideas and taking other people's ideas into account.

The therapist's role is to assist social learning. Instead of providing children with solutions to social difficulties, they are required to highlight the presence of a problem as and when it occurs. Children then have to identify the problem, and come up with their own solutions (with prompting from the adult if necessary) which are practiced before continuing with LEGO® building. Solutions that children suggest are practiced until they can do it, and the adult reminds children of strategies if similar difficulties arise in future. Adults take the usual role of enabling safe play.

For this study the sessions will follow the guidelines detailed in the abridged manual developed as part of the study setup (see fidelity analysis section 7.10) and based on (LeGoff *et al.*, 2014). Sessions will be run by an interventionist recruited from each school who will be trained by a professional from the local authority or from the research team. [name] and colleagues trained by her will provide training to these trainers who will then train all interventionists in the schools.

Groups will be made up of three to six children from a participating school, though they can go ahead with fewer numbers if children are absent on the day of a planned session. In the event that there are siblings within a school allocated to the intervention, schools will be requested to have them in separate groups to avoid bringing any dynamics from home into the groups. In schools where there are not enough children with ASD to make a complete group other children can join the group. This may include children who experience social difficulties that teachers believe may benefit from the intervention. This is the current policy of the local authorities and is the recommended method outlined by (LeGoff *et al.*, 2014). No identifiable data will be collected from these children, however they will be consented for being involved in the filming where applicable.

8.2. Care as usual

Participants allocated to 'usual support' will receive support as usual from their GPs, mental health and education professionals. Usual care is defined as normal practice for the school in question in addition to the usual support from the specialist teaching teams for autism in the area. This may include interventions such as the Picture Exchange Communication System (PECS), workstations, visual supports and schedules, and Social Stories. Services provided by the specialist teams include meeting and observing the child or young person in their setting, meeting their parents/carers and teachers/teaching assistants; liaising closely with colleagues in early years, transition team, health and social care; making recommendations to the setting about ways of supporting the child or young person; training in the use of different interventions, 1 to 1 working for specific interventions and attending reviews and meetings. They will also continue to provide reports and visual resources for home use and conduct monthly Drop In groups for parents. They will not receive the intervention or any extra support services from the research team.

8.3. Intervention Delivery

8.3.1. Treatment Protocol

As LEGO®-based therapy has only recently been established in the UK, it may be a new concept to the education professionals delivering the therapy. Therefore, we will follow a treatment protocol based on the work of [name] and co-applicant [name]. Co-applicant [name] and colleagues trained by her will provide training to key professionals at each Local Authority and in the research team on how to deliver LEGO®-based therapy sessions successfully, who will in turn provide the training to the education professionals allocated to deliver the therapy. As usual care can differ greatly for

each child, this arm will not follow a treatment protocol devised by the research team. Fidelity and acceptability of LEGO®-based therapy will be assessed using bespoke questionnaires which will be completed by the interventionist and associated teachers/ TAs.

8.3.2. Facilitator Training

The LEGO®-based therapy sessions will be delivered by an educational professional who is employed by each school allocated to the intervention arm. The educational professional may vary between the schools (such as a teacher, TA, SENCO etc). All professionals delivering the therapy will be trained in the study's LEGO®-based therapy protocols. To ensure the therapy sessions are being run correctly, schools will be selected at random to have their session's video recorded. These recordings will be observed by the research team for fidelity checks.

In order to deliver the LEGO®-based therapy for the I-SOCIALISE trial, the interventionists must:

- Have completed training in using the study's protocols for LEGO®-based therapy and be willing to use this protocol to deliver LEGO®-based therapy.
- Be aware of the possibility that a number of their sessions may be recorded, for research fidelity checks.
- Complete a fidelity checklist after each session.

8.4. Modifications or Variations in Delivery

The delivery of the LEGO®-based therapy may require modifications to account for differences in the children's demographic characteristics.

8.4.1. The child's age

Younger children may require a slower pace throughout the sessions. Additionally, we will group children together of appropriate ages to ensure that the sessions run smoothly and are straightforward for the children to follow.

8.4.2. Presence of Comorbid Mental Health Problems

The proposed research will not exclude explicitly on the basis of comorbidities. However, there may be occasions when the teacher/TA or parent/ guardian feels that a comorbid mental health condition may be made worse through trial participation. At these points the child may be withdrawn from the trial but we will continue to collect data from these children if appropriate. Those with comorbidities who are able to continue in the trial will receive the LEGO®-based therapy or usual care as planned. If the child/young person has a care coordinator, we will liaise with them about any specific needs or symptoms that we should consider and/or monitor throughout the intervention delivery.

8.4.3. Presence of Intellectual or Developmental Disabilities, Behavioural or Attention Problems

Some intellectual and developmental disabilities may mean we have to adapt intervention delivery. Where this is likely (e.g. children with ADHD), sessions will be adapted to help the

child complete the sessions. For example, this may involve more frequent breaks, or to have a trusted adult or other items present (e.g. a favourite toy) to comfort the child. Materials designed for younger children (e.g. with pictures and cartoons) may be used with adolescents who have intellectual disabilities.

8.4.4. Peer involvement

If there are not enough children meeting the eligibility criteria in the school allocated to the intervention arm, other children who may benefit from the therapy (e.g. those with social isolation issues) will be approached to attend the LEGO®-based therapy group. We will obtain informed consent from the parents of all children participating in the LEGO®-based therapy groups.

8.4.5. English as an additional language

We do not have funding for translators or to develop the study materials in other languages and so we will not be able to recruit where parents/guardians cannot understand written English, as they will not be able to provide fully informed consent or complete the study measures. Existing school services will be used for children with language and comprehension difficulties where appropriate.

9. Monitoring of Adverse Events

Possible harm as a result of the study is expected to be minimal but will be monitored according the Sheffield CTRU SOPs.

- 1. Questions relating to Adverse Events (AEs) will be used to record any untoward occurrence affecting the participant after each LEGO®-based therapy session by the interventionist and at the 20 week follow-up conducted by the research assistant.
- 2. Teachers and parents will be asked if they believe there have been any untoward events (above the child's usual behaviour) at the 20 week time point.
- 3. All AEs will be assessed for seriousness, and will be recorded as a Serious Adverse Event (SAE) if it;
 - Results in death
 - Is life-threatening
 - Requires hospitalisation or prolongation of existing inpatients hospitalisation
 - Results in persistent or significant disability or incapacity
- 4. The occurrence of adverse events during the trial will be monitored by the DMEC and the TSC.

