4.2.2. Parent questionnaires

- The Social Communication Questionnaire (SCQ) (Rutter, Bailey, & Lord, 2003) is a parent completed questionnaire derived from the Autism Diagnostic Interview–Revised (Lord, Rutter, & [name], 1994). The recommended cut-off to suggest it is likely an individual has ASD is 15. The SCQ has excellent sensitivity and reliability (Chandler et al., 2007). It will only be completed as an eligibility check prior to baseline – *baseline only*.
- 2. The Social Skills Improvement System (SSIS) (Gresham & Elliott, 2008) (further details in section 4.1).
- 3. Demographic information pertaining to the child and the parent will be collected. This will be done using a novel demographic information form *baseline only*.
- 4. The Strengths and Difficulties Questionnaire (SDQ) (Goodman, 1997), consisting of 25 items, will be used to measure the participating child's emotional and behavioural difficulties, distress and social impairment. Participating parents will mark a 3 point scale indicating if each statement is true, somewhat true, or certainly true (e.g. considerate of other people's feelings). This is an internationally recognised reliable and valid measure used in studies of children & adolescents including those with ASD.
- 5. The EQ-5D-Y (3L proxy version) (The EuroQol Group, 1990) is a five item generic preference-based measure of health-related quality of life that allows a proxy person to complete the measure for the participant. The use of this measure allows for the comparison between groups across a wide range of comparable dimensions and can therefore be used to perform a cost-utility analysis.
- 6. Bespoke resource use questionnaires, as described above, to capture the healthcare and non-health resource implications (including costs in the education sector, and costs of productivity loss and out-of-pocket expenditures for parents) attributable to the child's difficulties due to their condition.
- 7. Bespoke questionnaire to assess acceptability of the intervention 20 weeks only.
- 8. Custom designed questions (included in resource use form at 20 weeks) to assess any adverse events that may have been attributable to the trial intervention or usual care interventions. This will be developed in conjunction with our PPI representatives and the local authorities *20 weeks only*.

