4.2.3. Associated teacher/TA questionnaires

- 1. The Social Skills Improvement System (SSIS) (Gresham & Elliott, 2008) (further details in section 4.1).
- 2. The Strengths and Difficulties Questionnaire (SDQ) (Goodman, 1997), consisting of 25 items will be used to measure the participating child's emotional and behavioural difficulties, distress and social impairment. The TA will mark a three point scale indicating if each statement is true, somewhat true, or certainly true (e.g. considerate of other people's feelings). This is an internationally recognised reliable and valid measure used in studies of children & adolescents including those with ASD.
- 3. Bespoke resource use questionnaires have been developed by the research team to capture the resource implications of a child's behaviour at school and as a way of recording care and interventions as usual received in both arms.

4. Custom designed questions (included in resource use form at 20 weeks) to assess any adverse events that may have been attributable to the intervention. This will be developed in conjunction with our PPI representatives and the local authorities – 20 weeks only.

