4.2.4. Interventionist Teacher/ TA

- 1. Demographic information will be collected from the interventionist teachers using a novel demographic information form and relating to training and experience *baseline only*.
- A bespoke resource use questionnaire has been developed by the research team to capture the resource implications of running the LEGO®-based therapy sessions at school. This will include details on the make-up of the group and basic information on the non-ASD children such as relevant clinical diagnoses or behavioural issues – after each LEGO®-based therapy session.
- 3. Custom designed questions (included in session resource use form) to assess any adverse events that may have been attributable to the intervention *after each LEGO®-based therapy session*.
- 4. A fidelity checklist based on the existing treatment manual (LeGoff *et al.,* 2014) *after each LEGO®*-*based therapy session*.
- 5. A bespoke questionnaire to assess acceptability of the intervention. This questionnaire will be completed at the 20 weeks follow-up point. In addition to this, acceptability will be further assessed through qualitative interviews, conducted by telephone with a purposive sample of 20% of the interventionists across school types (primary/secondary and sociodemographic variables) post-intervention (n=12).

5. Study Design and Setting

We will conduct a multi-site (using three recruiting sites) pragmatic cluster RCT comparing LEGO®-based therapy and usual support with a control group receiving usual support alone. Usual support is defined as the existing support routinely provided for a child with ASD from educational services. This will be documented regularly in a systematic way for the duration of the study using a standardised recording tool that has been used successfully by our team in previous school based intervention studies. A pragmatic approach was selected as opposed to a more explanatory design to maximise the external validity of the trial and to allow us to examine the clinical effectiveness, sustainability and cost effectiveness of the intervention (Torgerson & Torgerson, 2008). This design will include a 10 month internal pilot study, a nested qualitative component, an examination of treatment fidelity and an economic evaluation.

Participants will be recruited via their school and treatment will take place in the child's school. Baseline and follow-up visits may take place in schools or participants' homes.

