5.1. Internal Pilot

The RCT will contain a ten month internal pilot. At the end of this period, the trial team will report to the NIHR on whether criteria for stopping have been met and whether the trial should continue. Sheffield CTRU will aggregate study data to assess feasibility of the research. Stop/Go criteria (see section 10.1) will be based on the feasibility of recruitment, retention and safety outcomes. We anticipate a recruitment rate of 12 children (six schools) per month. At ten months, we would have expected to recruit 120 children, and we will include a stopping criterion

of 75% of the recruitment target n=90. At this point, one third of the recruited participants would have reached the primary endpoint (n=40) and we would expect that 70% of the outcome measures will have been completed (n=28). As the trial exposes children with autism to a novel social situation, a Data Monitoring and Ethics Committee (DMEC) will review the data at the end of the pilot and throughout the trial for safety (see section 9.1). If there is evidence of harm due to the interventions or measures the trial may be stopped.

6. Eligibility Criteria

A number of inclusion and exclusion criteria must be met before a participant can be included in the trial. As I-SOCIALISE is a pragmatic trial, very few exclusion criteria will be applied. A detailed overview of the inclusion and exclusion criteria for the I-SOCIALISE trial is below.

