7.4.2 Method of implementing the allocation sequence

Randomisation and allocation to arms will be conducted remotely by a statistician from the Sheffield Clinical Trials Research Unit (CTRU). Once allocation is made, the trial managers will inform the schools of their group status by phone or email. We will request that the school schedules the 12 weekly intervention sessions as soon as the interventionist TA is trained to deliver LEGO®-based therapy to ensure that they will be delivered before the 20 week follow-up point. A letter with this information and details on what their particular allocation involves will

also be sent to the school after randomisation. This process has been examined and proved effective in a previous school based study on children with ASD (Wright *et al.*, 2016).

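### Adverse events are ascertained unequally by arm, and the 20-week teacher question is described in conflicting ways, so the wording and the source for any between-arm harm comparison need fixing

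*Protocol*

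**What the plan says.** Protocol Section 9, item 1, has adverse event questions completed "after each LEGO®-based therapy session by the interventionist and at the 20 week follow-up". Table 5 and Section 4.2.4 item 3 confirm that the interventionist fills in the session questions after every session. Section 7.4.2 sets the number of sessions: "We will request that the school schedules the 12 weekly intervention sessions". Of the usual-support arm, Section 8.2 says: "They will not receive the intervention or any extra support services from the research team". That arm therefore has no sessions, no interventionist and no session log, and no matching prospective log is described for it.

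Both arms share the 20-week questions, but the protocol describes these in different ways. Section 4.2.3 item 4 says the teacher questions are there "to assess any adverse events that may have been attributable to the intervention", and Section 7.5.3 uses the same attribution. Section 4.2.2 item 8 gives the parent questions a wider scope, covering events "attributable to the trial intervention or usual care interventions". Section 9 item 2 says that teachers and parents alike are asked at 20 weeks about any untoward event beyond the child's usual behaviour. It mentions neither attribution nor arm.

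The data have a use. Section 5.1 makes safety outcomes part of the Stop/Go criteria, has the DMEC review safety at the end of the pilot and throughout the trial, and adds: "If there is evidence of harm due to the interventions or measures the trial may be stopped".

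**The concern.** There are two separate problems.

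The first is unequal opportunity to record. Most of the expected events in Section 9.1 are distress, verbal abuse, aggression or running away. Section 9.1 itself treats aggression as a way in which children with ASD may express frustration, sadness or anxiety, so such events can occur in either arm. A log completed after each session will catch some that a single recall at 20 weeks misses. If the two kinds of record are added together, the LEGO arm shows more events even when the true rates are equal.

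The second is the teacher question. A teacher of a control child who is asked only about events attributable to the intervention has nothing to attribute. A teacher in a LEGO school answers a different question in effect, and Section 7.6 confirms that teachers know the allocation. Events that were never asked about cannot be recovered by any later analysis.

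At stake are the reading of safety by the DMEC, the safety part of the Stop/Go decision and the harms table in the final report.

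**Working it through.** The protocol states no adverse event rate, harm threshold or harm comparison, so there is no figure of its own to reproduce. The check has three parts.

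**1. Planned reporting occasions per child**

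| Source | LEGO arm | Usual support |
|---|---|---|
| Session log (Section 9 item 1; 4.2.4; Table 5), with 12 weekly sessions (7.4.2) | about 12 | 0 |
| Parent, 20 weeks (4.2.2; 9 item 2) | 1 | 1 |
| Teacher, 20 weeks (4.2.3; 9 item 2) | 1 | 1 |
| Total | about 14 | 2 |

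**2. The descriptions side by side**

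| Form | Description in Section 4 or 7 | Description in Section 9 |
|---|---|---|
| Teacher, 20 weeks | Attributable to the intervention (4.2.3, 7.5.3) | Any untoward event (item 2) |
| Parent, 20 weeks | Attributable to the intervention or to usual care interventions (4.2.2) | Any untoward event (item 2) |
| Session log | Attributable to the intervention (4.2.4) | Any untoward occurrence (item 1) |

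Under Section 9 item 2, teachers and parents answer the same question in both arms. Under 4.2.3 and 7.5.3, the teacher question does not fit a control child.

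**3. Illustration of the effect of pooling**

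All inputs here are assumptions, except the 12 sessions and the 20-week window. Let the true event rates be equal. Let r be the probability that an event is reported at 20 weeks, the same in both arms. Let q be the probability that a session log captures it (LEGO arm only), independently of recall. Each event is counted once.

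- Recorded share, control: r.
- Recorded share, LEGO: 1 − (1 − r)(1 − q).
- Ratio LEGO to control: [1 − (1 − r)(1 − q)] / r.

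For q, suppose sessions fall in 12 of the 20 weeks (0.6), 20% of events in those weeks happen at a session, and 90% of these are logged: q = 0.6 × 0.2 × 0.9 = 0.108.

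- r = 0.3: (1 − 0.7 × 0.892) / 0.3 = 0.3756 / 0.3 = 1.25
- r = 0.5: (1 − 0.5 × 0.892) / 0.5 = 0.554 / 0.5 = 1.11
- r = 0.7: (1 − 0.3 × 0.892) / 0.7 = 0.7324 / 0.7 = 1.05

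Letting q run from 0.1 to 0.8 over the same values of r widens the range to 1.04 (r = 0.7, q = 0.1) through 2.87 (r = 0.3, q = 0.8). The upper end needs session logs to catch 80% of all events over 20 weeks. With any q above 0 and r below 1, the ratio exceeds 1. If only the 20-week sources are used, with one wording in both arms, q drops out and the ratio is r / r = 1.00.

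**The case against.** The strongest reply is that a like-for-like channel already exists. Section 9 item 2 asks teachers and parents in both arms about any untoward event, and Section 4.2.2 has parents cover usual care. This stands. A reader might infer from the session logs that harms cannot be compared fairly at all; the protocol does not support that.

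Nor does it show that control-arm teacher reports will be near zero. Sections 4.2.3 and 7.5.3 summarise a form that is not in the document, 4.2.3 says it is still to be developed, and the dedicated safety section gives the arm-neutral version. The problem arises only if the form was built to 4.2.3 and 7.5.3. The protocol leaves that open.

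It is also true that no section plans to add session logs to 20-week reports, and that tabulation by source may be set out in an analysis plan that is not shown. A reader might infer that the DMEC will be misled. The documents do not support this either: the stopping sentence in 5.1 calls for a judgement about cause rather than a raw count, the DMEC includes an independent statistician (Section 12), and the TSC and DMEC review all SAEs, whether or not they are thought related (Section 9.1).

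Finally, session logging is sound monitoring. Choking on or swallowing bricks at a session has no control counterpart and should be recorded.

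What the objection does not answer is the conflict over what teachers are asked. That is data collection, which the protocol fixes, and an analysis plan cannot repair it afterwards.

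**Conclusion.** The point holds in a limited form. Two facts are in the protocol itself: session logs exist in the LEGO arm only (about 14 planned occasions against 2), and the 20-week teacher question is described inconsistently.

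Two consequences are conditional. If the teacher form follows 4.2.3 and 7.5.3, teacher reports are not comparable between arms. If session logs are counted in a between-arm comparison, recorded harm in the LEGO arm is biased upwards. The documents do not allow the size to be estimated; 1.05 to 1.25 times is an illustration that rests on assumed recall, timing and logging rates, and on equal true rates.

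A fair 20-week comparison is available if the arm-neutral wording is used. It would still be retrospective and come from reporters who know the allocation. The correction is worth making because safety outcomes feed the Stop/Go decision and a possible stop, and because it is cheap.

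**What to change.** 1. Reconcile Sections 4.2.2, 4.2.3, 7.5.3 and 9 to a single arm-neutral 20-week question for teachers and parents in both arms. Section 9 item 2 already supplies the wording.
2. Add one sentence saying that between-arm adverse event summaries, including those prepared for the DMEC, use the 20-week sources only.
3. Keep the session logs for safety monitoring and report them separately as LEGO-arm-only data.

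The cost is one form item and one or two sentences, with no new data collection. There is a small downside. Section 7.5 mentions parents who had completed follow-up before the prize draw was introduced, so forms were already being returned by this version. Any 20-week forms collected under a different wording cannot be harmonised; they should be identified as such in the safety summaries.
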